9.1.2.3. Disease Activity

Minimal Disease Activity

Minimal disease activity is calculated based on the scores from the Physician's Global Assessment of Disease Activity (Section 9.1.2.7), Parent's Global Assessment of Well-Being (Section 9.1.5), and the number of swollen joints as described in the SAP and Consolaro et al. 2012.

Inactive Disease

Inactive disease is indicated by the presence of all of the following (Wallace et al. 2011):

- No joints with active arthritis based on JADAS-27 (Section 9.1.2.1)
- No fever, rash, serositis, splenomegaly, hepatomegaly, or generalized lymphadenopathy attributable to JIA as assessed by the investigator
- No active uveitis as assessed by the investigator
- Normal erythrocyte (ESR) or hsCRP (i.e., within normal limits in the local laboratory or, if elevated, not attributable to JIA)
- Physician's Global Assessment of Disease Activity indicating no active disease (best possible score on scale [0]) (Section 9.1.5)
- Duration of morning stiffness ≤ 15 minutes

Remission

Remission is defined as inactive disease for at least 24 consecutive weeks (Wallace et al. 2012).

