6.10.2. Secondary Efficacy Analyses

Secondary efficacy and health outcomes analyses ([Table JAHV.6.4](#)) will be based on treatment periods with the respective population at each visit. The analysis method is described in [Table JAHV.6.5](#). There will be no adjustment for multiple comparisons.

Table JAHV.6.4. Description and Derivation of Primary, Secondary Efficacy Endpoints and Health Outcomes

Measure	Description	Variable	Derivation/Comment	Imputation Approach if with Missing Components
Disease flare	
Disease flare is defined as a worsening of $\geq 30\%$ in at least 3 of the 6 PedACR core criteria for JIA and an improvement of $\geq 30\%$ in no more than 1 of the criteria from the patient's condition at randomization baseline. In disease flare-ESR, ESR measure is used as acute-phase reactant in the core criteria.
 
 • If either the number of joints with active arthritis or the number of joints with limitation of motion are used in the calculation of flare for a study visit, then a minimum worsening of at least 2 active joints or 2 joints with limitation of motion must be present. • An active joint is defined as a joint with swelling or, in the absence of swelling, limitation of motion accompanied by pain on motion and/or tenderness. • If either the Physician's Global Assessment of Disease Activity or the Parent's Global Assessment of Well-Being are used in the calculation of flare for a study visit, then a minimum worsening of at least 20 mm in 0-100 mm visual analogue scale (VAS) must be present. • If ESR is used in the definition of "flare" and counts towards worsening, then the second value for ESR used in the calculation must be above the upper limit of normal for ESR (>20 mm/hour). 	Time to disease flare	
The details of disease flare calculation are documented in separate disease flare and PedACR response calculation algorithm document.
 
Calculation: Date of disease flare-ESR minus date of randomization+1
	
Component is missing if baseline or postbaseline value is missing. LOCF will be applied for post baseline missing values. If more than 3 components are missing, there will not be sufficient information; thus, the patient will be considered as a non-flare patient.

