
Inactive disease
	
Inactive disease is indicated by the presence of all of the following (Wallace et al. 2011):
 
 No joints with active arthritis based on JADAS-27 No fever, rash, serositis, splenomegaly, hepatomegaly, or generalized lymphadenopathy attributable to JIA as assessed by the investigator No active uveitis as assessed by the investigator Normal erythrocyte (ESR) or hsCRP (ie, within normal limits in the local laboratory or, if elevated, not attributable to JIA) Physician's Global Assessment of Disease Activity indicating no active disease (best possible score on scale [0]) Duration of morning stiffness less than 15 minutes In inactive disease analysis as secondary endpoint, ESR measure is used as acute-phase reactant measure. 	
Proportion of patients who achieved inactive disease
	
 Step 1: If joint with active arthritis isn't 0, stop; else Step 2: If there is fever, rash, serositis, splenomegaly, hepatomegaly, or generalized lymphadenopathy attributable, stop; else Step 3: If uveitis, stop; else Step 4: If ESR>20, stop; else Step 5: If physician's global assessment of disease activity isn't 0, stop; else Step 6: If stiffness >15min, stop; else Step 7: Conclude the patient achieved inactive disease status. 	
Missing if any component is missing. NRI will be applied to missing data.

Secondary Efficacy Endpoint Analyses

Measure	Description	Variable	Derivation/Comment	Imputation Approach if with Missing Components
Minimal disease activity	Minimal disease activity is calculated based on the scores from the Physician's Global Assessment of Disease Activity, Parent's Global Assessment of Patient's overall Well-Being, and the number of swollen joints as described in Consolaro et al. 2012.	Proportion of patients who achieved minimal disease activity	
 • if physician's global assessment of disease activity ≤ 3.5, and • if parent's global rating of patient's overall well-being ≤ 2.5, and • if swollen joint count ≤ 1, then conclude the patient reaches minimal disease activity; all else conclude the minimal disease activity is not reached. 	
Component is missing if baseline or postbaseline value is missing. LOCF will be applied for post baseline missing values.
 
If all components are missing after LOCF, NRI will be applied to missing data.

Secondary Efficacy Endpoint Analyses

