6.10.3. More Supplementary Analysis

For the composite measures/endpoints which have acute-phase reactant ESR or CRP as component, in general, the ESR version of derivation will be used as the main version of derivation for the first and secondary analysis. The hsCRP version of derivation will be used as a supplementary version for the supplementary analysis and will be provided for selected visits only, as defined in [Table JAHV.6.6](#) and [Table JAHV.6.7](#).

Table JAHV.6.6. Description of the Use of ESR and hsCRP in Endpoints Derivation

Endpoint	Version	Calculation difference between ESR version and hsCRP version	Measure	Type of the endpoint	Analysis
flare	ESR version	Derivation refer to Table JAHV.6.4	time to flare	primary endpoint	primary analysis
	ESR version	Derivation refer to Table JAHV.6.4	proportion of patients who have disease flare	secondary endpoint	secondary analysis
PedACR response	ESR version	Derivation refer to Table JAHV.6.4	proportion of patients who achieve PedACR response	secondary endpoint	secondary analysis
	PedACR (hsCRP) response	Derivation logic is same as ESR version	proportion of patients who achieve PedACR-hsCRP response	supplementary	supplementary analysis
JADAS-27	ESR version	Derivation refer to Table JAHV.6.4	change from baseline of JADAS-27	secondary endpoint	secondary analysis
	hsCRP version	Derivation logic is same as ESR version, use Norm hsCRP=(hsCRP-10)/10 instead of NormESR	change from baseline of JADAS-hsCRP-27	supplementary	supplementary analysis
inactive disease	ESR version	Derivation refer to Table JAHV.6.4	proportion of patients who achieve inactive disease status	secondary endpoint	secondary analysis
	hsCRP version	Derivation logic is same as ESR version, use hsCRP>3 instead of ESR>20	proportion of patients who achieve inactive disease status (hsCRP)	supplementary	supplementary analysis
disease remission	ESR version	Derivation refer to Table JAHV.6.4	proportion of patients who achieve disease remission status	secondary endpoint	secondary analysis
	hsCRP version	Derivation logic is same as ESR version, use hsCRP>3 instead of ESR>20	proportion of patients who achieve disease remission status (hsCRP)	supplementary	supplementary analysis

Abbreviations: ESR = erythrocyte sedimentation rate; hsCRP = high-sensitivity C-reactive protein; JADAS = Juvenile Arthritis Disease Activity Score; PedACR = Pediatric American College of Rheumatology.

Table JAHV.6.7. Description hsCRP Related Supplementary Analysis

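### The SAP's steps for inactive disease fail every ESR above 20 and omit the exception, in both documents' definitions, for elevations not due to JIA

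*SAP*

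**What the plan says.** Protocol 9.1.2.3 lists the acute-phase item of inactive disease as "Normal erythrocyte (ESR) or hsCRP (i.e., within normal limits in the local laboratory or, if elevated, not attributable to JIA". The description column of the Inactive disease row in SAP Table JAHV.6.4 (Section 6.10.2) carries the same allowance: "within normal limits in the local laboratory or, if elevated, not attributable to JIA". That row also fixes the reactant for the secondary endpoint: "In inactive disease analysis as secondary endpoint, ESR measure is used as acute-phase reactant measure".

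The derivation column turns the definition into seven steps. The ESR step reads "Step 4: If ESR>20, stop; else". It has no attribution clause, although the step for systemic features keeps one in shortened form: "Step 2: If there is fever, rash, serositis, splenomegaly, hepatomegaly, or generalized lymphadenopathy attributable, stop; else". For the supplementary hsCRP version, SAP Table JAHV.6.6 gives "Derivation logic is same as ESR version, use hsCRP>3 instead of ESR>20", again without the exception.

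Remission is defined as inactive disease lasting at least 24 weeks without a break. The SAP derives it from the inactive-disease status at six earlier visits: Visits 7 to 12 for an assessment at Visit 13, and so on up to Visits 11 to 16 for Visit 17. Protocol Table JAHV.8 lists inactive disease and remission as baricitinib-versus-placebo comparisons in the double-blind withdrawal (DBW) period, by logistic regression.

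**The concern.** The definition and the steps disagree about one group: children who meet every other criterion and whose ESR is above 20 mm/hour for a reason other than JIA. Both documents define them as inactive, and Step 4 makes them not inactive.

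Nothing in the documents resolves the conflict. The flare and PedACR rows refer to a separate algorithm document, but the inactive-disease row does not, so its steps are the only specification given. The SAP revision history does not announce a simplification. Neither document says where the investigator's view of an elevated ESR would be recorded.

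At stake are two secondary comparisons. They would be reported under a definition that the program does not apply. Remission is the more exposed of the two, because it needs six passing visits in a row.

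**Working it through.** **Which way the step acts.** The documents use 20 mm/hour as the upper limit of normal for ESR (flare definition, Protocol 10.3.3.1 and SAP Table JAHV.6.4). On that limit:

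| ESR at the visit | Definition | Step 4 |
|---|---|---|
| 20 or below | passes | passes |
| above 20, due to JIA | fails | fails |
| above 20, not due to JIA | passes | fails |

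Patients who pass Step 4 are therefore a subset of those who pass the definition. Taken alone, the step can lower the rate or leave it unchanged, but cannot raise it.

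**Size.** The plan states no inactive-disease or remission rate, so there is no figure of its own to reproduce. Let p be the share of otherwise-inactive visits with a non-JIA ESR above 20. The documents do not give p. I assume 3%, 5% and 10%; zero is also possible.

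- Inactive disease at one visit: the share wrongly failed is p.
- Remission at one assessment (one fixed six-visit window, visits independent): 1 − (1 − p)^6.
- Never in remission in any window, for a child inactive at all ten visits from Visit 7 to Visit 16: with s = 1 − p, the chance of at least one run of six passing visits among ten is s^6 × (1 + 4(1 − s)), so the loss is 1 − s^6 × (1 + 4p).

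| p | s^6 | One window fails | Never in remission |
|---|---|---|---|
| 3% | 0.833 | 16.7% | 1 − 0.833 × 1.12 = 6.7% |
| 5% | 0.735 | 26.5% | 1 − 0.735 × 1.20 = 11.8% |
| 10% | 0.531 | 46.9% | 1 − 0.531 × 1.40 = 25.6% |

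If the elevation persists within a child instead of striking visits independently, the loss in every column is only about p.

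**In patients.** Take an assumed true rate of 40%, 64 patients per arm and p = 5%. Inactive disease at a visit becomes 0.40 × 0.95 = 38.0%, a loss of 64 × 0.40 × 0.05 = 1.3 patients. Remission at one assessment, with independent visits, becomes 0.40 × 0.735 = 29.4%, a loss of 64 × 0.40 × 0.265 = 6.8 patients.

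**An opposing departure for remission.** Visits 7 to 12 fall at Weeks 4, 8, 12, 16, 20 and 24. They span 24 − 4 = 20 weeks, and the assessment visit at Week 28 is not checked. The other four windows have the same shape. This is looser than the 24-week definition and pushes the remission rate up.

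**The case against.** The strongest reply is that a fixed cut-off is objective and reproducible, is applied alike in both blinded arms, and avoids a subjective judgement on each raised value. That is a fair reason to prefer the rule. It is not a reason to keep a definition that says something else, and the SAP does not say that the change was intended.

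Three limits stand.

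- **Frequency.** The documents give no rate of non-JIA ESR elevation in otherwise-inactive children. Protocol 3.3 reports infections in about half of the baricitinib-exposed adults in the RA program, which makes such elevations plausible but is not an ESR frequency.
- **Local limits.** The definition refers to the local laboratory's limits. At a site with a limit below 20, Step 4 would pass some values that the definition calls elevated. The subset argument therefore rests on the documents' own limit of 20 mm/hour.
- **Comparison between arms.** If p is the same in both arms, the ratio of rates does not change. The effect is not nil, because SAP 6.1.4 bases inference on the odds ratio: assumed remission rates of 40% and 20% give 2.67, and multiplying both by 0.735 (29.4% and 14.7%) gives 2.42.

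A reader might go further in three ways that the documents do not support.

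- That both rates are understated. With p unknown this is not shown, and for remission the 20-week windows act the other way.
- That a single raised ESR rules out remission. A failure at Visit 7 touches only the Visit 13 assessment and one at Visit 16 only the Visit 17 assessment. Only Visits 11 and 12 lie in all five windows.
- That the step favours one arm. Nothing in the documents shows that p differs between arms.

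**Conclusion.** The concern holds as a mismatch between the defined and the derived endpoint. Followed as written, Step 4 classes as not inactive some children whom the protocol and the SAP's own description class as inactive.

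With 20 mm/hour as the limit of normal, the step taken alone can only lower inactive disease and the remission rate that depends on it. The loss at a single visit is p. For remission it lies between about p and the tabulated figures, depending on whether elevations persist or are independent, and on whether one assessment or all five are considered. All of these rest on an assumed p and include zero. The net direction for remission is open.

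Only secondary endpoints, and the supplementary hsCRP versions of them, are involved. Time to flare and the sample size are not affected.

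**What to change.** Settle the rule before unblinding, so that it is not chosen with results in view.

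- **If the investigator's attribution of a raised ESR is recorded:** change Step 4 so that a patient stops there when ESR exceeds 20 mm/hour, unless the elevation is recorded as unrelated to JIA. Say where that record is held. ESR is assayed at the site (Protocol Appendix 2), so the investigator sees the value. The cost is one SAP line and some reliance on investigator judgement.
- **If it is not recorded:** delete the exception from the definition, report the endpoint as requiring ESR of 20 mm/hour or less, and note that this is stricter than the cited criteria. The cost is a wording change and a slightly stricter endpoint. This is likely to be the more practical route if attribution would have to be collected retrospectively: SAP Version 2 was approved in March 2022, ahead of the primary outcome lock.
- **For the supplementary hsCRP version:** state hsCRP of 3 mg/L or less as the definition. Protocol Appendix 2 withholds hsCRP results from sites after Visit 9, so investigators cannot attribute those values in the DBW period.

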9.1.2.7. Physician’s Global Assessment of Disease Activity

The Physician’s Global Assessment of Disease Activity is used to assess the patient’s current disease activity, as it relates to their signs and symptoms. The instrument uses a 21-circle VAS ranging from 0 to 10 (using 0.5 increments) where 0 = “no activity” and 10 = “maximum activity” (Filocamo et al. 2010).

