9.1.5. Health Outcomes

Childhood Health Assessment Questionnaire

The Childhood Health Assessment Questionnaire (CHAQ) assesses health status and physical function in children with juvenile arthritis over the past week, which the parent or legal guardian completes, regardless of the age of the patient.

The CHAQ has 2 indices – the Disability Index and the Discomfort Index. The Disability Index contains 30 items grouped into the following 8 domains (not including assistive devices/aids questions): dressing and grooming, arising, eating, walking, hygiene, reach, grip, and activities. The domains are averaged to calculate the Disability Index (physical function). Each item is scored from 0 to 3 (0 = no difficulty; 1 = some difficulty; 2 = much difficulty; 3 = unable to do or not applicable). A higher score indicates worse physical function (Singh et al. 1994). Data will be captured on an electronic tablet.

The Discomfort Index of the CHAQ includes (Ruperto et al. 2001):

- Parent’s Global Assessment of Well-Being
 - This is a component of the PedACR core response set as well as the JADAS-27
 - The instrument is a 0 to 100 mm VAS assessing the current level of well-being where 0 = “Very well” and 100 = “Very poor”.
- Pain assessment due to illness
 - This instrument is a 0 to 100 mm VAS that assesses the current level of pain severity over the past week, where 0 = “No pain” and 100 = “Very severe pain”.

Childhood Health Questionnaire-Parent Form 50

The Childhood Health Questionnaire-Parent Form 50 (CHQ-PF50) is a generic observer-reported instrument designed to capture the health-related quality of life of children and adolescents (from 5- to 18-years of age), as well as the impact of the child's disease on the caregivers (HealthActCHQ 2013). The CHQ-PF50 is completed by the caregivers and has been validated for use in patients with JIA (Ruperto et al. 2001).

The CHQ-PF50 consists of 50 questions covering 14 health concepts: Global Health; Physical Functioning; Role/Social Limitations-Physical; Role/Social Limitations-Emotional/Behavioral; Bodily Pain/Discomfort; General Behavior; Mental Health; Self-Esteem; General Health Perceptions; Change in Health; Parental Impact-Emotion; Parental Impact-Time; Family-Activities; and Family-Cohesion.

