Limited range of motion joint count	Number of joints with limited range of motion in 69 joints	Change from baseline of limited of motion joint count	Calculation: Change from baseline: observed limited range of motion joint count at visit minus baseline limited range of motion joint count	Missing if baseline or postbaseline value is missing. LOCF will be applied for post baseline missing values.
Physician's global assessment of disease activity (VAS)	The Physician's Global Assessment of Disease Activity is used to assess the patient's current disease activity, as it relates to their signs and symptoms. The instrument uses a 21 circle VAS ranging from 0 to 10 (using 0.5 increments) where 0 = "no activity" and 10 = "maximum activity" (Filocamo et al. 2010).	Change from baseline of physician's global assessment of disease activity	Calculation: Change from baseline: observed score at visit minus baseline score	Missing if baseline or postbaseline value is missing. LOCF will be applied for post baseline missing values.
Parent's global assessment of overall well-being measured by CHAQ (10cm VAS)	The parent is generally asked to make a global assessment of the child's overall well-being on a 10 cm VAS, with anchors of '0 = very good' and '10 = very poor', which is located at the bottom of the Childhood Health Assessment Questionnaire (CHAQ) questionnaire	Change from baseline of parent's global assessment of overall well-being	Calculation: Change from baseline: observed score at visit minus baseline score	Missing if baseline or postbaseline value is missing. LOCF will be applied for post baseline missing values.

Secondary Efficacy Endpoint Analyses

Measure	Description	Variable	Derivation/Comment	Imputation Approach if with Missing Components

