JADAS-27	
The JADAS-27 score is a validated composite disease activity measure for JIA (Consolaro et al. 2012). Recently, the scoring system was adapted to use the 27-joint count (Bazso et al. 2009) and hsCRP or ESR for the inflammatory marker component (Nordal et al. 2012). The JADAS 27 includes the following joints: cervical spine, elbows, wrists, metacarpophalangeal joints (from first to third), proximal interphalangeal joints, hips, knees, and ankles. In JADAS-27 analysis as secondary endpoint, ESR measure is used as acute-phase reactant measure,
	
Change from baseline of JADAS-27 score
	
JADAS-27 score (0-57) will be determined based on 4 components:
 
 • PHY: Physician’s Global Assessment of Disease Activity (0-10 VAS) • PGA: Parent’s Global Assessment of Patient’s overall Well-Being (0-100 mm VAS) • Joint27: Number of joints with active disease (27-joint assessment) • ESR (mm/hr) 
Calculation:
 
NormESR: Normalized ESR (0-10) NormESR=(ESR-20)/10
 
Scaled PGA= scaled Parent’s Global Assessment of Patient’s overall Well-Being (0-10) Scaled PGA=PGA/10
 
JADAS(ESR)27=PHY+ScaledPGA+Joint27+NormESR
 
Change from baseline: observed JADAS(ESR)-27 at visit minus baseline JADAS-27
	
Missing if baseline is missing: For observed value, missing if all the components are missing. LOCF will be applied for post baseline missing value. If at least one component is non-missing, LOCF will be applied on the missing components prior to LOCF being applied to the composite score

Secondary Efficacy Endpoint Analyses

Measure	Description	Variable	Derivation/Comment	Imputation Approach if with Missing Components
Pain (VAS)	The pain assessment item will be collected from the CHAQ.	Change from baseline of pain vas score	Calculation: Change from baseline: observed score at visit– baseline score	Missing if baseline or postbaseline value is missing. LOCF will be applied for post baseline missing value.

Abbreviations: CHQ-PF50 = Child Health Questionnaire-Parent Form 50; ESR = erythrocyte sedimentation rate; hsCRP = high-sensitivity C-reactive protein; JADAS = Juvenile Arthritis Disease Activity Score; JIA = juvenile idiopathic arthritis; LOCF = last observation carried forward; NRI = nonresponder imputation; PedACR = Pediatric American College of Rheumatology; VAS = Visual Analog Scale.

Table JAHV.6.5. Description of Analysis Period and Analysis Method of Secondary Endpoint and Health Outcome

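### SAP Table JAHV.6.4 gives the Parent's Global two scales (0-10 and 0-100 mm), so no single stored score fits both the minimal disease activity rule and the JADAS-27 formula as printed

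*SAP*

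**What the plan says.** The Parent's Global appears in four places.

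- **Protocol 9.1.5 (CHAQ Discomfort Index):** "The instrument is a 0 to 100 mm VAS assessing the current level of well-being where 0" is the best state and 100 the worst.
- **SAP 6.10.2, Table JAHV.6.4, Parent's Global row:** the parent rates "overall well-being on a 10 cm VAS, with anchors of" 0 and 10.
- **Same table, JADAS-27 row:** the input is listed as a 0-100 mm score and converted by "Scaled PGA=PGA/10". The total is stated to run from 0 to 57.
- **Same table, minimal disease activity row:** the rule requires a Physician's Global of at most 3.5, then "overall well-being ≤ 2.5, and" at most one swollen joint. It states no unit and does not use the scaled variable that the JADAS-27 row defines.

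The Physician's Global is described consistently as 0 to 10 in half-point steps (Protocol 9.1.2.7; SAP Table JAHV.6.4, its own row and the JADAS-27 row). The disease flare row, however, sets one minimum for whichever global is used: "minimum worsening of at least 20 mm in 0-100 mm visual analogue scale (VAS) must be present". The protocol leaves this minimum to the SAP (Synopsis, 9.1.1 and 10.3.3.1). The SAP places the details of the flare calculation in a separate algorithm document, which is not among the documents. The minimal disease activity and JADAS-27 rows make no such referral.

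**The concern.** A derivation table should let two programmers arrive at the same number. Here the minimal disease activity rule makes sense only if the parent score is held as 0-10, and the JADAS-27 formula only if it is held as 0-100. Whoever programs both must supply a conversion that the plan does not print.

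Both are secondary endpoints compared between baricitinib and placebo from Week 16 to Week 44: minimal disease activity by logistic regression, JADAS-27 by ANCOVA with a supplementary MMRM. A wrong scale would misclassify patients on the first or nearly remove the parent's view from the second. Change from baseline in the Parent's Global, also a secondary endpoint, has ambiguous reporting units. Its test is unaffected, because a constant factor does not alter an ANCOVA p-value.

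The flare row matters for a different reason. Flare is the primary endpoint, it is diagnosed on site in real time (Protocol 5.1.4 and 9.1.1), and it ends participation (Protocol 5.4). The site calculation and the analysis calculation must therefore use the same units.

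**Working it through.** **Inputs (SAP Table JAHV.6.4).** Physician's Global 0-10; Parent's Global 0-10 or 0-100 mm; 27 joints; normalised ESR 0-10; minimal disease activity cut-offs 3.5 (physician) and 2.5 (parent); flare minimum 20 mm of 100 mm.

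**Step 1: reproduce the plan's own figure.** JADAS-27 maximum = physician + parent/10 + joints + normalised ESR = 10 + 100/10 + 27 + 10 = 57. This equals the stated upper limit, so the JADAS-27 row is right if the physician score is 0-10 and the parent score is 0-100 mm.

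**Step 2: apply both printed rules under each stored scale for the parent score.**

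| Parent score stored as | Minimal disease activity parent cut-off | JADAS-27 maximum |
|---|---|---|
| 0-100 mm | 2.5/100, which is 0.25 on a 0-10 scale | 10 + 10 + 27 + 10 = 57 |
| 0-10 | 2.5/10, which is 25 mm | 10 + 1 + 27 + 10 = 48 |

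Neither line satisfies both rules. The first makes the cut-off ten times stricter. The second cuts the parent term from a range of 0-10 to 0-1 and loses 9 points from the maximum.

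**Step 3: worked patients.**
- Physician 2, one swollen joint, parent mark at 20 mm. Stored as 2.0, 2.0 ≤ 2.5 and the patient has minimal disease activity. Stored as 20, 20 > 2.5 and the patient does not.
- Physician 5, parent mark at 50 mm, 10 joints, ESR 40. Stored as 50: 5 + 50/10 + 10 + (40 − 20)/10 = 22.0. Stored as 5: 5 + 5/10 + 10 + 2 = 17.5.

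**Step 4: an illustration of the cut-off, on an assumption that is not in the documents.** Suppose parent scores among responders were exponential with mean 20 mm (range 10 to 30 mm). The share meeting a cut-off c is 1 − exp(−c/mean).
- c = 25 mm: 71% (92% at mean 10, 57% at mean 30).
- c = 2.5 mm: 12% (22% at mean 10, 8% at mean 30).

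This covers the parent item only. It caps the endpoint, because all three items must be met. It shows direction and is not an estimate for this trial.

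**Step 5: the flare minimum.** 20 mm of 100 mm is 20/100 of the range, which on a 0-10 scale is 0.20 × 10 = 2.0 points, or four half-point steps. A Physician's Global rising from 2 to 7 changes by 5 points and passes this minimum once converted. If the bare number 20 were compared with the raw 0-10 score, no rise could pass, since the largest possible is 10. The table does not print the conversion that separates these two outcomes.

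**The case against.** The strongest reply is that each row reads correctly if its unit is respected. A 10 cm line is a 100 mm line, so there is only one instrument. The JADAS-27 row declares its input, prints its conversion and gives a range that reproduces exactly. The parent cut-off of 2.5 agrees with the 0-10 description elsewhere in the same table, and it sits beside a physician cut-off of 3.5 that is plainly on 0-10. On this view only a unit label is missing.

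Part of that stands. The instrument is not in doubt, and the JADAS-27 row needs no change. But the two descriptions lead to stored numbers that differ tenfold, and the minimal disease activity row says neither which one it takes nor that it takes the scaled one. Applied as printed to the score as the protocol describes it, the rule misclassifies patients. That is more than a missing label.

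The reply succeeds on flare. A reader might infer that the Physician's Global can never count toward flare, and hence that the primary endpoint is wrong. The documents do not support this. The threshold names its own 0-100 mm scale, and reading it as one fifth of the range is natural. The conversion may already be written in the separate algorithm document. The 30% worsening criterion itself does not depend on scale, so only the minimum is involved.

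**Conclusion.** The minimal disease activity rule is wrong as written for a Parent's Global held on 0-100 mm, and it cannot be reconciled with the JADAS-27 formula on any single stored scale. The size is a factor of ten: either the parent cut-off becomes 2.5 mm instead of 25 mm, or the JADAS-27 parent term falls tenfold and the maximum is 48 instead of 57. This conflict stands even if the flare row is set aside.

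The conclusion assumes that 2.5 was meant on a 0-10 scale, which the adjacent physician cut-off and the Parent's Global row both suggest.

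The flare row is a secondary matter: a conversion is missing for the Physician's Global, and no error in the primary endpoint is shown. Nor should a reader infer that any result is already wrong. The documents do not show how the scores are stored or programmed, so the effect on results is unknown.

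**What to change.** In SAP Table JAHV.6.4:

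1. Declare one stored scale for the Parent's Global, 0-100 mm. This agrees with Protocol 9.1.5 and reproduces the 0-57 range.
2. Correct the Parent's Global measure row to 0-100 mm.
3. In the minimal disease activity row, apply the cut-off to the scaled variable: PGA/10 ≤ 2.5.
4. Leave the JADAS-27 row as it is.
5. In the disease flare row, print the existing 20 mm minimum re-expressed for the Physician's Global (2.0 on its 0-10 scale). This restates the same threshold and sets no new one.
6. Reconcile the separate flare and PedACR algorithm document and the on-site flare calculation with these units.

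The cost is a few lines of SAP wording and a programming check before database lock. No new data are needed, and the design and the primary test do not change.
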